9.2.2. Exclusion Criteria

Table 3. Summary of Exclusion Criteria

Exclusion Criteria	Assessment Period	Operational Definition	Rationale/Validated Source
Stroke or history of stroke	[Baseline]	At least one medical claim with an ICD-10- CM diagnosis code with evidence of stroke.	This study is intended to be generalizable to SCD patients. Patients with a history of stroke may rely on RBC transfusions for disease management and will therefore be excluded.
Pregnancy	[Baseline]	At least one medical claim with an ICD-10- CM diagnosis code with evidence of pregnancy	This study is intended to be generalizable to SCD patients and this is a common exclusion for RCTs. Individuals with SCD may receive RBC transfusions to ensure adequate oxygenation of the fetus during pregnancy. Voxelotor is not indicated during pregnancy.
Hemodialysis or history of hemodialysis	[Baseline]	At least one medical claim with an ICD-10- PCS procedure code with evidence of hemodialysis.	Patients with a history of hemodialysis may rely on RBC transfusions for disease management and will therefore be excluded.
Hematopoietic stem cell transplantation (HSCT) or gene therapy or history of HSCT or gene therapy	[Baseline]	At least one medical claim with an ICD-10-PCS procedure code with evidence of HSCT or gene therapy.	Patients with a history of HSCT may rely on RBC transfusions for disease management and will therefore be excluded. After HSCT or gene therapy, their disease may be markedly improved.

Renal transplant or history of renal transplant	[Baseline]	At least one medical claim with an ICD-10- PCS procedure code with evidence of renal transplant.	Patients with a history of renal transplants may rely on RBC transfusions for disease management and will therefore be excluded.
Liver transplant or history of liver transplant	[Baseline]	At least one medical claim with an ICD-10-PCS procedure code with evidence of liver transplant.	This study is intended to be generalizable to SCD patients. Patients with a history of liver transplants may rely on RBC transfusions for disease management and will therefore be excluded.
Iron overload - Exploratory Objective 3 Subgroup Only	[Baseline]	At least one medical claim with an ICD-10- CM diagnosis code with evidence of iron overload	To assess incident events in follow-up for Exploratory Objective 3

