9.7.2. Baseline Balance

PS methods will be used to account for baseline balance of covariates between the treated group and matched controls. PS adjustment allows for the inclusion of a pre-defined comprehensive list of confounding covariates to ensure comparable exposure and referent groups, avoiding non-convergent issues of standard outcome models. PS models estimating the ATT will be considered for this analysis. An iterative approach to estimating the PS will be used.

PS Estimation

Potential covariates that affect treatment decisions or outcomes and are eligible for inclusion in the PS model are listed in Table 5.³⁰ Potential confounding covariates will be assessed for balance at baseline using absolute standard differences (ASD). Covariates with an ASD > 0.1 will be considered imbalanced and will be included in a PS model fit using logistic regression. With this approach, the PS will be modeled as the conditional probability of receiving voxelotor given the selected covariates for each individual. The PS modeling will be performed blinded of any outcome to ensure endpoints will not be assessed before a PS method is selected. Diagnostic criteria used to assess PS model estimate are described below and in Table 6. Multiple iterations of the PS model estimation may be performed depending on diagnostic evaluation results.

Use of PS in Baseline Confounder Balance

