Multiple PS methods will be considered and a step-wise approach will be used to select the most appropriate method. PS matching, in which voxelotor-exposed individuals are matched to unexposed patients using variable-ratio (1:2) greedy nearest neighbor matching with a caliper, will be the primary approach.³¹ If the sample size falls below the minimum required sample size for the primary and secondary endpoint to be 80% powered during the matching process, weighting methods, such standardized mortality/morbidity ratio (SMR) weights, will be evaluated for their suitability and to preserve sample size of the exposed group. With the SMR approach, weights for the voxelotor group are equal to 1; weights for the referent arm are defined as PS/(1-PS). The distribution of SMR weights will be reviewed; truncation and trimming will be considered to account for extreme weights. If neither PS model type is deemed appropriate, a non-ATT model (overlap weights) will be considered. With the overlap approach, overlap weights are defined as 1-PS in the voxelotor arm; weights for individuals in the referent arm are defined as the PS. The distribution of overlap weights will be reviewed to evaluate the appropriate trimming threshold. PS-matching and weighting methods will be further described in the SAP.

Diagnostic Evaluation of PS Methods

An *a priori* list of diagnostic criteria will be set to ensure analytic assumptions are met before a PS method is selected. For example, ASD will be used to assess the comparability of the groups before and after the application of PS methods.³² Observations for any covariate leading to zero cells in either group may lead to an inadequate overlap between groups in

their PS distributions. Therefore, collapsing similar categories within variables if there are categories with frequencies <10% to minimize concerns for non-positivity will be considered. Further, variables with substantial non-positivity may be removed from the model (i.e., covariables with very low or zero values in either group). Patients with missing information for covariables may be excluded or imputed from the analysis set depending on the degree of missingness and the variable. When applicable, a robust variance estimator may be utilized in the outcome model(s) to account for the weighted design. Demographics and baseline clinical characteristics of patients within each study group will be described before and after the applications of PS adjustment.

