The diagnostic results will be presented to the study team who will provide a final confirmation that all the necessary criteria have been satisfied. The inferential analysis phase will only begin after sign-off of the final protocol by the study team, certified by the Principal investigator (PI). More information on the methods used to balance baseline covariates can be found in SAP and in Table 6 below.

Table 6. Diagnostic Checklist

#	Diagnostic	Description	1
1	Confirm positivity of variables	PS distribution will be visually inspected and overlap in all areas of the PS distribution will be confirmed.	
		Additionally, any patients with an observation for covariates not meeting the positivity assumption and may be considered outliers. Further detail on methodology is available in SAP.	
2	Confirm PS model fit	Any covariate with no variability (i.e., a constant value across all observations) will be removed from the PS model. The PS model will be determined as not overfit if each covariate contains ≥ 12 exposed subjects. ³³ Collinear covariates will be defined as any covariates with a Pearson correlation coefficient greater than or equal to 0.7. ³⁴ Collinear variables may be removed from the PS model if large standard errors are observed because including them may lead to biased coefficient estimates. If removed, the model will be refitted. ³⁵	
3	Confirm baseline confounder balance	Balance of all potential confounders (i.e., covariates) will be confirmed for voxelotor vs referent patients. Covariate balance will be defined as an ASD ≤ 0.10. ³⁶ Balance of these variables will still be confirmed after PS matching. Should any variables with small residual imbalance remain, balance may be deemed acceptable if the variable is not a predictor of the outcome among the referent group (defined as an ASD < 0.10 when comparing the risk of the outcome to those with the variable versus those without it). This determination will be made by clinical experts or key opinion leaders on the study team. Evaluation of imbalance in outcome prediction will only be	

1/2	0	23	Dec	am	har	20	124

		conducted once at the end of the diagnostic sub-phase if all other diagnostic criteria are met. Variables with residual imbalance across the exposure and referent groups that are associated with the outcome (e.g., baseline Hb) will be included as an independent variable in the subsequent outcome model.	

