Required 1-year minimum follow-up	Two subgroup analyses have been proposed to evaluate bias introduced by differential follow-up. First, a subgroup analysis of patients with a minimum of 1-year of follow-up will be performed to evaluate the impact of informative censoring.	To address the impact of informative censoring and differential follow-up
Matched censoring	If meaningful differences in follow-up time are observed, matched censoring will be performed to assess the impact of differential follow-up between the exposed and referent group for the primary objective. Bias due to differential follow-up can arise when the reasons for participants dropping out or being lost to follow-up are related to both the treatment and the outcome. Matched censoring mitigates this bias by censoring all patients within a matched set (i.e., patients that have been matched by PS matching) at the earliest time in which a patient in the set was censored. In the context of 1:2 PS matching, where each exposed patient is matched to two referent patients, the matched set will consist of at most three individuals. Thus, matched censoring in this scenario involves censoring data for all three individuals in a matched set at the earliest observed censoring time among them.	To address the impact of informative censoring and differential follow-up
Stratification by number of RBC transfusions in baseline	The number of RBC transfusions PPPY in baseline will be categorized and the primary objective will be reported separately for those categories. This analysis will be performed for all objectives.	To understand the effect of the treatment on high-risk subgroups.
Subgroup analysis by Hb level	The primary analysis will also be performed on a subgroup of patients with Hb values at baseline. A separate PS model will be utilized for this subgroup.	To understand the effect of the treatment on high-risk subgroups and patients with available baseline data.
Subgroup analysis by prior medications	A subgroup analysis will be performed on patients who received hydroxyurea, crizanlizumab, L-glutamine, and/or ESA in baseline the exposed and referent groups.	To understand the effect of other SCD treatments.

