Because this study does not include an active comparator as a control group, CEM will be used to select the index date of matched controls on the initiation of voxelotor for exposed patients. All exposed patients will be selected prior to controls to preserve sample size. Sampling bias may be introduced by prioritizing exposures, but the impact is limited due to a larger pool of untreated control patients than potential exposures. There may be differences in patient characteristics dependent on when patients enter the study population (i.e., initiating voxelotor versus periods without treatment for matched controls). However, PS methods will be utilized to control for observed baseline confounding between the exposed and referent groups. Linked Ouest data will be used to evaluate Hb levels in baseline (an important diagnostic criterion for RBC transfusions). Feasibility analyses will be conducted prior to implementation to assess the number of patients in this study with available Hb data. Assuming a significant number of patients will not have Hb data in baseline, a sensitivity analysis has been proposed to assess the primary outcome among patients with this lab data. However, there may be differences in the frequency of Hb testing between the exposed and control group, relative to when patients enter the study cohort. For most subgroup analyses, the PS obtained from the overall study cohort PS model will be used for PS adjustment. However, for the subgroup of patients with non-missing Hb values in baseline, the PS model will be re-fit and will include an additional covariate (mean Hb value). Depending on the utilization of other SOC treatments in both the exposed and control groups, other subgroup analyses may be conducted. Additionally, the primary analysis will be as-treated, which includes discontinuation of voxelotor as a censoring criterion in the exposed group. This creates potential for confounding via differential censoring between the exposed and referent groups. However, to account for these potential differences in follow-up time, matched censoring will be used to censor matched controls on the date of their voxelotor match's discontinuation date as a sensitivity analysis.

A summary of the potential limitations of the RWD in this study and the mitigation strategies that will be applied is provided in Annex Table 3.

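### Most subgroup analyses reuse the overall-cohort propensity score, and balance is not required to be confirmed inside each reported stratum, so residual confounding there could go unseen

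*Protocol*

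**What the plan says.** Section 9.7.2 builds the PS in the cohort matched on age and calendar date. Entry to the model depends on whole-cohort imbalance: "Covariates with an ASD > 0.1 will be considered imbalanced and will be included in a PS model fit using logistic regression". The first-choice method is PS matching: "variable-ratio (1:2) greedy nearest neighbor matching with a caliper, will be the primary approach". Table 6, item 3, then requires: "Balance of all potential confounders (i.e., covariates) will be confirmed for voxelotor vs referent patients", with balance defined as ASD of 0.10 or less. It does not say whether this is repeated within subgroups.

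Table 7 in section 9.7.3 plans a stratified analysis, extended to all objectives: "The number of RBC transfusions PPPY in baseline will be categorized and the primary objective will be reported separately for those categories". It also plans subgroups by prior and concomitant medication. For the Hb subgroup it adds: "A separate PS model will be utilized for this subgroup". For the rest, section 9.9 settles the matter: "For most subgroup analyses, the PS obtained from the overall study cohort PS model will be used for PS adjustment". The only condition the protocol sets for running a subgroup is a minimum sample size, with detail left to the SAP.

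The Exploratory Objective 3 population is also a cut of the cohort. Table 3 removes patients with baseline iron overload, chelation, delayed hemolytic transfusion reaction or alloimmunization, under labels such as "Iron overload - Exploratory Objective 3 Subgroup Only".

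**The concern.** A PS that balances the whole cohort is only guaranteed to balance a stratum if the model is right for that stratum. Two features of this plan weaken that guarantee.

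- **The entry screen uses the overall ASD.** A covariate with a positive imbalance in one stratum and a negative one in another can average to below 0.1 and never enter the model.
- **A covariate entered as a main effect gets one coefficient.** If channelling to voxelotor on that covariate differs by stratum, the overall score can balance it on average and still leave it unbalanced in each stratum.

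The overall diagnostic would pass in both cases. A difference in effect between patients with many and few baseline transfusions could then be confounding that looks like effect modification. These results are meant to be interpreted: Table 7 gives understanding of high-risk subgroups as the purpose, and Annex Table 3 cites stratification by prior treatment as mitigation for hydroxyurea as a known confounder.

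**Working it through.** The plan gives no figure for balance within subgroups, so there is none to reproduce. The benchmark is its own ASD limit of 0.10. Every simulation setting below is an assumption.

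**1. How cancellation works.** Take two equal strata with similar spread and the same treated-to-control ratio. The overall ASD is then roughly the average of the two. With within-stratum values of −0.17 and +0.17: 0.5 × (−0.17) + 0.5 × 0.17 = 0. The overall check passes and both strata fail.

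**2. Simulation with an omitted interaction.** 925 patients; stratum S with prevalence 40%; confounder X ~ N(0.4·S, 1). The log-odds of treatment are −1.7 + 0.5·S + 0.4·X + k·X·(S − 0.4). The PS is fitted with main effects only. Matching is greedy 1:2 with a caliper of 0.2 SD of the logit; 150 replicates. The slope on X is 0.4 + 0.6k in stratum 1 and 0.4 − 0.4k in stratum 0.

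| k | Slopes, S=1 / S=0 | Overall ASD | ASD, S=1 | ASD, S=0 | Replicates with absolute ASD > 0.10 (overall; S=1; S=0) |
|---|---|---|---|---|---|
| 0 | 0.40 / 0.40 | 0.013 | 0.029 | −0.003 | 0%; 14%; 15% |
| 0.3 | 0.58 / 0.28 | 0.013 | 0.087 | −0.060 | 0%; 42%; 27% |
| 0.5 | 0.70 / 0.20 | 0.015 | 0.113 | −0.074 | 0%; 56%; 27% |

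The overall check never failed. With no interaction, mean within-stratum imbalance is near zero and the 14–15% is chance. With an interaction, the strata breach the limit in 27–56% of replicates.

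A fourth run left S out of the score, and 27–29% of replicates breached within strata. But S itself then had an overall ASD of 0.246 after matching, which Table 6 would catch, so I place no weight on it.

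**3. Other settings.** With 200 treated, 800 controls, a 50% stratum and channelling of 0.5 ± 0.2 log-odds per SD, overall ASD was 0.07 and within-stratum values were −0.13 and +0.23. In a further simulation with channelling differing by ±0.2, overall ASD was 0.01 and the strata −0.17 and +0.17. With no interaction, the strata were at about 0.

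**4. What the fix achieves.** In that further simulation, re-matching within the stratum and adjusting for what remained moved the spurious stratum effects from about −0.13 and +0.15 to 0.03 and 0.00. These are on the simulation's own outcome scale, not transfusions per year. Matching alone can leave something behind. In the 200/800 design at ±0.2, refitting and re-matching left 0.02 and 0.13; re-matching on the reused overall score left −0.04 and 0.18. The outcome-model adjustment is therefore a necessary part of the fix.

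**5. Chance imbalance.** In a half-size subgroup of the planned 185 and 370 (93 and 185), the chance SD of a standardized difference is √(1/93 + 1/185) = 0.127. The probability of exceeding 0.10 in absolute value is P(|Z| > 0.10/0.127) ≈ 43% for a covariate balanced only in expectation. This would occur whichever score is used, so it is not a cost of reusing the overall one. It does bear on how a failed check should be handled.

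**The case against.** **SAP detail.** Sections 9.7.2 and 9.7.3 leave matching, weighting and subgroup criteria to the SAP, which is not at hand, and within-subgroup diagnostics are ordinary SAP content. This stands as far as silence goes: absence of a stratum-level check from the protocol would not be a finding alone. What remains is a stated choice, reuse of the overall score, combined with a stated entry rule based on whole-cohort imbalance.

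**Matched sets.** A reader might infer that the 1:2 sets are cut apart by stratum. The protocol does not say so. It says the score is reused, which is compatible with re-matching or re-weighting inside the subgroup. If sets were cut, and stratum membership were independent within sets, the share of treated patients keeping at least one control would be 1 − (1 − p)²: 75% at p = 50%, 44% at p = 25%. That loses patients and pairing but does not by itself create bias.

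**Necessary confounding.** A reader might also infer that confounding must return. It need not. The subgroup-defining variables are listed candidate covariates in Table 4, and Annex Table 3 says hydroxyurea will be in the model. If the score is correct and contains the stratifying variable, balance holds in expectation within strata (k = 0 above). No figure in the documents shows that channelling differs by stratum.

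**Scope of the check.** Table 6 does not limit its balance check to the whole cohort; it is silent on scope.

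**Existing safeguards.** Section 9.7.3 already puts unbalanced covariates into the primary and Objective 1.1 models and allows this for Objective 3. That is a real safeguard, but it works only if imbalance is looked for in the patients being analysed.

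**Conclusion.** The point holds as a cheap improvement. The protocol fixes reuse of the overall score for most subgroups, screens covariates on overall imbalance, and does not require its own 0.10 limit to be confirmed where stratum results are reported. Residual within-stratum confounding is therefore possible and would go unseen. Under moderate assumed differences in channelling, mean within-stratum ASD was between 0.06 and 0.23 in absolute value while the overall value was 0.01 to 0.07; without such differences it was about zero. The size rests wholly on that assumption.

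The reach is limited to the Table 7 strata and subgroups other than Hb and, conditionally, Exploratory Objective 3. The protocol does not say whether the Objective 3 population is among those that reuse the overall score, so the documents do not support saying that the whole objective is compromised. The overall primary estimate is not affected.

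**What to change.** For each Table 7 stratum or subgroup, and for the Objective 3 population, state that:

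1. Patients are re-matched or re-weighted within the subgroup. The overall score may be reused, with a refit where numbers allow. Under weighting, a reused score gives each patient the same weight as before (trimming aside), so the refit or step 3 must do the correcting.
2. The Table 6 ASD check is applied and reported inside the subgroup.
3. Covariates above 0.10 there are included in that subgroup's outcome model. For Objective 3, change 'may' to 'will' in section 9.7.3.
4. Strata with remaining imbalance are flagged, not suppressed. Chance alone can push many covariates past 0.10 in small strata, so suppression would remove results for reasons unrelated to confounding.

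The cost is a few lines of wording and re-running the matching code per subgroup. Some patients lose their match, and subgroup intervals widen slightly.

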9.10. Other Aspects

Missing data will be handled depending on the amount (e.g., more than x% of patients missing a value for a variable) and mechanism (e.g., missing completely at random, missing at random, or missing not at random) of missingness. Missingness will be documented only for variables for which a value would be expected for all observations, such as age or sex, and not for variables where the absence of a value can be reasonably interpreted as the absence of a condition (e.g., diagnoses). Furthermore, whenever applicable, a category for missing values will be reported for categorical variables. For more details on how missing data is imputed see companion SAP.

10. PROTECTION OF HUMAN PARTICIPANTS

10.1. Patient Information

This study involves data that exist in deidentified/anonymized structured format and contain no patient personal information.

10.2. Patient Consent

As this study involves deidentified/anonymized structured data, which according to applicable legal requirements do not contain data subject to privacy laws, obtaining informed consent from patients by Pfizer is not required.

10.3. Institutional Review Board (IRB)/ Ethics Committee (EC)

This study was determined to be exempt under 45 CFR § 46.104(d)(4) by WCG IRB's IRB Affairs Department that reviewed this study under the Common Rule and applicable guidance on August 23, 2024.

